### 3.0 Previous Human Studies

The Biotronik CLS algorithm has been studied extensively in the clinical setting. Notable findings include improvements in heart rate response during mental stress reliable tracking of the sympathetic tone and excellent performance despite beta-blocker therapy. In addition, most patients prefer CLS pacing as opposed to traditional accelerometer-based pacing in a ratio of 2:1 after sequential randomization to both pacing modes. However, there is almost no data supporting the use of this algorithm in the congenital heart disease population. In addition, there is a very limited amount of clinical data (essentially limited to isolated case reports) describing the use of CLS after epicardial pacemaker implantation.

### 4.0 Inclusion/Exclusion Criteria

Inclusion criteria:

- o Congenital heart disease
- o Simple, moderate, or complex congenital heart disease
- o Adolescent or adult age group (age >14 and <65 years)
- o Significant sinus node dysfunction
- o Atrial pacing percentage >70%

- o Intrinsic dysfunction resulting from congenital lesion or cardiac surgery •
- Secondary sinus node dysfunction due to antiarrhythmic drug therapy
- o Existing, fully functional Biotronik pacemaker or ICD with CLS capability
- o Epicardial or transvenous route of pacemaker implantation

Exclusion criteria:

- o Unable to complete cardiopulmonary exercise testing (CPET) o
- Contraindication to CPET
- o Decreased mental capacity or known psychiatric disorder
- o Congestive heart failure, NY HA class IV
- o Total atrial tachyarrhythmia burden >20%

## 5.0 Enrollment]Randomization

Patient Enrollment: The treating physician will identify potential subjects with a previously implanted Biotronik pacemaker and present a brief overview of the study; if the subject is interested, the study will be described in detail. Informed consent will be obtained by the investigator after discussing the study, including the voluntary nature of participation and notification the subject can withdraw at any time. Ample time for questions and answers will be allowed. The investigator will give the subject and his/her legal guardian the opportunity to take the consent home to think about it more, with the option to call or meet with the investigator to ask additional questions. If the subject and/or his/her parent/legal guardian agree to participate, the investigator will ask them to sign a written, informed consent and assent. A copy of the assent and consent will be given to the subject and/or his/her parent/legal guardian.

Randomization Procedure: This will be a single-blind placebo-controlled randomized crossover study with 2 treatments: CLS-on versus CLS-off (accelerometer only). Each enrolled patient will receive both treatments for 3 months. The order of treatments will be randomized 1 :1.

## 6.0 Study Procedures

All patients enrolled in the study will undergo the following baseline assessment and data collection:

- Demographics (age, gender, race/ethnicity)
- Review of data confirming the presence of sinus node dysfunction with chronotropic incompetence (prior exercise stress test and/or Holter monitor results)
- Review of clinical history, including age at diagnosis, congenital diagnosis, surgical history, and cardiac device implant procedure
- Antiarrhythmic drugs prescribed and the respective dosages
- Prior ECG and echocardiography and advanced imaging reports

## Randomization

[figure not shown]
There will be a 50:50 randomization, with half the subjects randomized to CLS-on then CLS-off, and half randomized to CLS-off then CLS-on.

Subjects previously receiving rate-responsive pacing with CLS that are randomly selected to CLS-on will continue with the identical programmed parameters. For subjects not previously receiving rate-responsive pacing with CLS that are randomly selected to CLS-on nominal programming will be utilized with a base rate of 60 beats per minute.

Subjects will then initiate treatment A (CLS-on or CLS-off) in a blinded fashion. During the testing period, subjects will be tracked with the implanted device accelerometer to quantify physical activity. At 3 months, all subjects will undergo testing as noted below.

- 24 hour Holter monitoring with spectral analysis
- Cycle-ergometer stress with cardiopulmonary gas exchange analysis
- Free form activities with cardiopulmonary gas exchange analysis (staircase, walking, sweeping, suitcase lifting with right and left arms, etc.)
- ANSAR testing (hand grip, Valsalva, deep breathing, and orthostatic challenge)
- Mental stress test with continuous electrocardiographic recording
- Quality of life questionnaire (SF-36/Somerville index)

After 3 months of treatment A, subjects will be reprogrammed to treatment B. Tracking of physical activity with the device accelerometer will continue during this period. After 3 months of treatment B, repeat testing will be repeated as described above. At the conclusion of the study, patients will be asked which pacing mode is preferred.

Patients will be followed during both treatment phases per usual clinical routine. Patients who experience significant symptoms (extreme fatigue, debilitating palpitations, or other clinically relevant symptoms) will be evaluated by their treating physician. Subjects that have any adverse events during treatment A will discontinue treatment A and immediately crossover to treatment B. Subjects with events during treatment B will be removed from the study and unblinded. Further treatment will be determined by the treating physician.

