## 2.0 Rationale and Specific Aims

Improvement in sensor-based rate adaptation for sinus node dysfunction is needed in the CHD population. Emerging data suggest that greater aerobic capacity and heart rate

reserve are independently associated with superior outcomes in this population. Improvements in these parameters can be expected with the use of the Biotronik CLS algorithm and this pacing system may therefore be particularly well-suited to patients with CHD.

The Specific Aims of this protocol are:

Primary Aim: To determine the performance of CLS for CHD patients after both transvenous and epicardial pacemaker implantation

Hypothesis: CLS after either pacemaker implantation strategy will result in equivalent improvements in autonomic control of chronotropic response as compared to standard sensor based rate modulation

Primary outcome: Objective change in autonomic modulation of heart rate while randomized to CLS pacing with mental stress and ANSAR testing

Secondary outcomes: Increase in aerobic capacity, non-sedentary behavior, and quality of life while randomized to CLS pacing

This will be a single-blind (blinded subjects) randomized cross-over study, in which each patient will receive treatment A (CLS-on or CLS-off) for 3 months followed by treatment B (CLS-0ff or CLS-on).

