#### 10.0 Statistical Considerations

##### Sample Size Estimation and Power Analysis

The primary endpoint of this randomized controlled 2x2 cross-over trial will be to measure the influence of autonomic function on heart rate response, and to show an equivalent response for both epicardial and transvenous CLS pacemaker systems. The objective of this study is to evaluate changes in heart rate in response to the CLS algorithm versus a standard accelerometer during various tests of autonomic function. Previous studies of adults with chronotropic incompetence using the CLS algorithm have demonstrated a mean increase in heart rate of  $16.1 \pm 1.1$  beats/minute during mental stress with CLS-on versus  $5.8 \pm 0.6$  beats/minute with standard accelerometer ( $p<0.001$ ).

A further pilot study using ANSAR demonstrated a mean increase in 12.5 beats/minute during isometric hand-grip with CLS-on versus 2.9 beats/min with standard accelerometer ( $p=0.004$ ), 13.2 beats/minute during deep breathing versus 2.9 beats/minute ( $p=0.004$ ), 16.0 beats/minute during Valsalva maneuver versus 4.5 beats/minute ( $p=0.004$ ), and 14.9 beats/minute for postural change versus 6.2 beats/minute ( $p=0.039$ ). The results of the prior pilot study are summarized below.

ANSAR HEART RATE	Baseline	DOD-CLS	DDD	T test	Wilcoxon test
Resting	55.8	70.0	60.8	<0.001	0.004
Isometric Handgrip	59.4	71.9	62.3	<0.001	0.004
Deep Breathing	58.0	71.2	60.9	<0.001	0.004
Valsalva maneuver	57.1	73.1	61.6	<0.001	0.004
Postural Change	58.1	73.0	64.3	0.015	0.039

From Pavri et al. Circulation 2006;114;II 749. 

A two-sided t-test achieves 80% power to infer that the mean difference is not 0 when the total sample size of a cross-over design is 40 (or 81% when n=24 and 96% when n=30) assuming a 5% type I error. The actual difference and the square root of the within mean square error are assumed to be 10. Considering a drop-out rate of 30%, a total of 57 patients will need to be enrolled to achieve the target sample number.

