## Statistical Analysis Plan

Descriptive statistics, including means, standard deviations, and ranges for continuous variables, as well as percentages and frequencies for categorical variables, will be provided to describe the study sample. Differences between group means for continuous variables will be examined using ANOVA or Kruskal-Wallis Test. Point estimates along with the corresponding p-values and 95% confidence intervals will be reported. The adjusted p-values and the corresponding 95% confidence interval will be reported for multivariate analyses. Statistical analysis will be done with JMP version 12.0 (SAS Corporation, Cary, NC).

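### Treatment order is not stratified by lead route although route equivalence is part of the primary endpoint, and no period or route term is named; a cheap fix for a modest, conditional risk

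*Combined protocol and SAP*

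**What the plan says.** Section 5.0 states that "The order of treatments will be randomized 1 :1". The Randomization text in section 6.0 repeats this: "There will be a 50:50 randomization, with half the subjects randomized to CLS-on then CLS-off, and half randomized to CLS-off then CLS-on". Neither place gives a stratification factor, a block size or a method of generating the list.

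Lead route is nevertheless part of the main question. The hypothesis in section 2.0 is that "CLS after either pacemaker implantation strategy will result in equivalent improvements in autonomic control of chronotropic response", and the primary endpoint in section 10.0 includes the aim "to show an equivalent response for both epicardial and transvenous CLS pacemaker systems". Section 4.0 admits either route ("Epicardial or transvenous route of pacemaker implantation") and sets no quota or expected share.

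On analysis, the Statistical Analysis Plan says "Differences between group means for continuous variables will be examined using ANOVA or Kruskal-Wallis Test". It also mentions multivariate analyses without listing their covariates. Period, sequence and route are not named as model terms.

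**The concern.** In a cross-over each patient serves as his or her own control. If the two orders are equally filled, a shift common to everyone between period 1 and period 2 cancels from the overall CLS effect. Balance over the whole trial does not secure this within a subgroup, and here the CLS effect has to be estimated separately in epicardial and transvenous patients and then compared. If order is forced to be equal overall, an excess of one order in one route produces the opposite excess in the other. The two errors then have opposite signs and add in the route difference.

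A period shift is possible in this design. The same mental-stress, ANSAR and exercise tests are repeated about 3 months apart, devices are reprogrammed with no stated washout, and an adverse event can shorten the first period. At stake are the accuracy of the route-specific CLS estimates if period is ignored, and their precision if it is modelled.

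**Working it through.** **The plan's own figures.** The plan gives no figure for the route comparison. Its power statement is for a single overall comparison: "A two-sided t-test achieves 80% power to infer that the mean difference is not 0" at a total of 40, with "The actual difference and the square root of the within mean square error are assumed to be 10". With SE = s_w × √(2/N), s_w = 10 and N − 2 degrees of freedom, power is 96.2% at N = 30 (stated 96%), 91.1% at N = 24 (stated 81%) and 99.2% at N = 40 (stated 80%). Only the figure for 30 reproduces. That mismatch does not bear on this point. The within-subject SD of 10 is used below for scale.

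**Inputs.**
- From section 10.0: 40 evaluable patients, 30% drop-out, 57 enrolled, within-subject SD 10, planned CLS difference 10 beats/min.
- Assumed: 12 epicardial and 28 transvenous completers. The documents give no split.
- Assumed: a period effect π (period 2 minus period 1) of 2 to 5 beats/min. The documents give none.

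**Step 1: chance of imbalance.** Let K be the number of epicardial patients who have CLS-on first. Under simple randomisation K is Binomial(12, 0.5). If only the overall 20:20 is forced, K is hypergeometric (12 drawn from 40, of whom 20 have CLS-on first). The chance of 8:4 or worse in either direction is 38.8% and 30.1% respectively. The chance of a split of 2:1 or worse at several epicardial sizes:

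| Epicardial completers | Simple | Balanced overall only |
|---|---|---|
| 8 | 29% | 24% |
| 10 | 34% | 27% |
| 12 | 39% | 30% |
| 15 | 30% | 19% |
| 20 | 12% | 3% |

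The point does not depend on choosing 12, but it fades as the routes approach equal size.

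**Step 2: shift if period is ignored.** The CLS-on minus CLS-off difference has mean τ − π when CLS-on comes first and τ + π when it comes second. The unadjusted mean over m patients, n1 and n2 in the two orders, is therefore off by π × |n1 − n2| / m.
- Epicardial, 8:4: π × 4/12, which is 0.67 at π = 2 and 1.67 at π = 5.
- Transvenous, 12:16: π × 4/28 in the other direction, which is 0.29 and 0.71.
- Route difference: 0.67 + 0.29 = 0.95 (from unrounded terms) and 1.67 + 0.71 = 2.38.

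**Step 3: scale.**
- Epicardial SE = √(200/12) = 4.08, so the shift is 0.67/4.08 = 0.16 to 1.67/4.08 = 0.41 SE.
- Route-difference SE = √(200/12 + 200/28) = 4.88, so the shift is 0.95/4.88 = 0.20 to 2.38/4.88 = 0.49 SE.

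Imbalance in either direction is equally likely, so the expected shift over randomisations is zero.

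**Step 4: cost if period is modelled within route.** The estimate is then unbiased, and its variance is inflated by m² / (4 × n1 × n2). At 8:4 this is 144 / (4 × 32) = 1.125, or √1.125 = 1.06 on the SE. Averaged over the distributions in Step 1 for 12 patients, the inflation is about 8% (balanced overall only) to 12% (simple).

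**Step 5: what stratification achieves.** Blocks of 4 within route cap the order difference at 2 patients as randomised. Among 12, the largest shift at π = 5 is then 5 × 2/12 = 0.83 beats/min. Drop-out weakens this. If 17 epicardial patients (12/0.7 = 17.1) are enrolled 9:8 and a random 12 complete, 8:4 or worse still has about a 13% chance.

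**The case against.** The strongest reply is that the missing period term is the real defect. Once period is fitted within route the bias is gone without stratification, and what remains is a modest loss of precision. That stands, and it is why the model comes first in the fix.

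The upper end of the assumed period effect is also open to challenge. Section 10.0 reports whole heart-rate rises under the standard accelerometer of 2.9 (handgrip), 2.9 (deep breathing), 4.5 (Valsalva), 5.8 (mental stress) and 6.2 (postural change) beats/min. A shift of 5 would exceed three of these five. Exercise familiarisation would act mainly on aerobic capacity, which is a secondary outcome. This stands too: 5 should be read as an upper illustration.

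It can also be said that ANOVA may be meant as a cross-over ANOVA, since the sample-size text refers to a within-subject mean square error. That is possible, but the analysis text speaks of differences between group means and names no terms, so a period adjustment cannot be assumed.

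A reader might infer that the epicardial group is known to be small. The documents do not say so; it follows only that at least one route has 20 or fewer of 40. A reader might also infer that stratification costs nothing. Only subjects are blinded, so small blocks could let staff guess upcoming orders. Finally, a figure under the Randomization heading is not shown, so stratification depicted only there cannot be excluded.

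**Conclusion.** The point holds in a limited form. The text does not stratify order by route, route equivalence is part of the primary endpoint, and no period or route term is named. The shift needs three things together: a real period effect, a chance imbalance within a route, and an analysis that ignores period. With 12 epicardial patients, an 8:4 split and a period effect of 2 to 5 beats/min, all of them assumptions, it is 0.7 to 1.7 beats/min for the epicardial estimate and 0.95 to 2.4 for the route difference. Both are below half a standard error, against a planned CLS effect of 10.

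A reader might conclude that the CLS effect or the route comparison is biased as designed. The documents do not support that. The expected shift is zero, the overall CLS effect is protected to the extent that order is balanced overall, and a period term removes the bias. The case for acting is that the imbalance falls on a primary comparison, cannot be undone after randomisation, and is cheap to limit. Priority is minor to moderate.

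**What to change.** 1. In the Statistical Analysis Plan, specify a within-subject cross-over model for the primary outcome with treatment, period, route and treatment-by-route, and let the period effect differ by route. Report the CLS effect within each route and the difference between routes, with confidence intervals. This removes the bias.

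2. In section 5.0 and the Randomization text of section 6.0, randomise order 1:1 stratified by lead route only, in permuted blocks of varying size from a concealed list. This protects precision. A further factor such as prior CLS use should not be added: it would make four strata among about 57 patients, and many blocks would stay incomplete.

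The cost is two lists in place of one and a few sentences of text. Devices are already implanted at enrolment, so route is known before randomisation and accrual is unaffected. Two limits remain. There is a small risk of predictable allocation because staff are not blinded, which varying block sizes and concealment reduce. Balance is also protected at enrolment, not among completers after the planned 30% drop-out, so the model terms are needed whether or not order is stratified.

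### Programming rules are written for CLS-on only, so as planned a heart-rate difference between modes cannot be attributed to the sensor alone

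*Combined protocol and SAP*

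**What the plan says.** Section 5.0 (Randomization Procedure) defines the comparison as "2 treatments: CLS-on versus CLS-off (accelerometer only". That is the only description of CLS-off there, and Section 10.0 adds only that the comparator is a standard accelerometer.

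Section 6.0 (Randomization) has two programming rules, both conditional on CLS-on:

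- Earlier CLS users: "Subjects previously receiving rate-responsive pacing with CLS that are randomly selected to CLS-on will continue with the identical programmed parameters".
- Patients without earlier CLS: "randomly selected to CLS-on nominal programming will be utilized with a base rate of 60 beats per minute".

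The switch between periods is described only as "After 3 months of treatment A, subjects will be reprogrammed to treatment B"; no parameter is named. The text gives no maximum sensor rate for either mode. Neither the baseline data list nor the three-month test list in Section 6.0 includes programmed settings.

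The primary outcome in Section 2.0 is "Objective change in autonomic modulation of heart rate while randomized to CLS pacing with mental stress and ANSAR testing". It does not say which resting rate, if any, the change is measured from. Section 4.0 requires atrial pacing more than 70% of the time.

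**The concern.** The stated objective in Section 10.0 is to compare one sensor with another. That needs everything except the active sensor to be the same in a patient's two periods. The rules can break this in either direction. A patient who comes in on accelerometer pacing with a base rate other than 60 is moved to nominal programming in CLS-on, while CLS-off may stay at the old rate. An earlier CLS user keeps individual settings in CLS-on, while the CLS-off settings are unspecified.

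Randomising the order does not help, because unequal settings would belong to the mode and not to the period. Only subjects are blinded, and no blinding of the staff who program the device is described. A programmed floor or ceiling can influence the measured rate in heavily paced patients, so the primary heart-rate contrast and the secondary aerobic-capacity contrast could both be affected. Because recording of settings is not planned, an imbalance might be recoverable only from clinical device records.

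**Working it through.** **1. The rules applied to each kind of patient**

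| Patient | CLS-on | CLS-off | Match required? |
|---|---|---|---|
| Earlier CLS user | own existing parameters | accelerometer; other settings not stated | no |
| No earlier CLS | nominal, base rate 60 | accelerometer; other settings not stated | no |

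Order can matter too. For a patient without earlier CLS, CLS-on first resets the device, and the reset values may carry into CLS-off. With CLS-off first, the earlier clinical values may stay. The text allows either.

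**2. The planned effect**

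Section 10.0 states: "The actual difference and the square root of the within mean square error are assumed to be 10". For a 2x2 crossover, SE = 10 × √(2/N) with N − 2 degrees of freedom, two-sided 5%. This gives power of 91.1% at N = 24 (plan: 81%), 96.2% at N = 30 (plan: 96%) and 99.2% at N = 40 (plan: 80%). Only the middle figure reproduces. That is a separate matter; what is needed here is the 10 bpm benchmark.

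**3. Sensitivity to the resting rate, from the pilot table in Section 10.0**

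The quoted pilot increases reproduce as differences from the table's baseline column, for example handgrip 71.9 − 59.4 = 12.5 and 62.3 − 59.4 = 2.9. The table labels the comparator column DDD. The contrast from each mode's own rest is (CLS − 70.0) − (DDD − 60.8).

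| Test | CLS − DDD | From own-mode rest | Resting gap as share of CLS − DDD |
|---|---|---|---|
| Rest | 70.0 − 60.8 = 9.2 | – | – |
| Handgrip | 71.9 − 62.3 = 9.6 | 1.9 − 1.5 = 0.4 | 9.2/9.6 = 96% |
| Deep breathing | 71.2 − 60.9 = 10.3 | 1.2 − 0.1 = 1.1 | 9.2/10.3 = 89% |
| Valsalva | 73.1 − 61.6 = 11.5 | 3.1 − 0.8 = 2.3 | 9.2/11.5 = 80% |
| Postural change | 73.0 − 64.3 = 8.7 | 3.0 − 3.5 = −0.5 | 9.2/8.7 = 106% |

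In the pilot, nearly all of the contrast was already present at rest. The table reports no programmed rates, so it cannot show whether programming or the sensor produced that gap. It shows only that a contrast of this type is sensitive to whatever sets the resting rate.

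**4. Upper bound on the bias (inputs assumed)**

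Bias in mean absolute heart rate ≤ share of patients with unequal base rates × gap. The documents give neither input. With a 10 bpm gap, all in one direction:

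- 25% of patients: 0.25 × 10 = 2.5 bpm
- 50%: 0.50 × 10 = 5 bpm
- 100%: 1.00 × 10 = 10 bpm

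If settings match, the bias is 0. If 25% differ upwards and 25% downwards, the net is 2.5 − 2.5 = 0.

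**5. What an offset could do to the test**

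Assume no sensor effect, absolute heart rate analysed, and a constant offset that passes through in full. At N = 40, SE = 10 × √(2/40) = 2.24. An offset of 2 bpm then gives a significant result 14% of the time and an offset of 5 bpm 59%, against a nominal 5%. At N = 24 the figures are 10% and 38%.

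**The case against.** The best defence is that both arms are named by their sensor and the objective is stated in sensor terms, so being reprogrammed to treatment B naturally means switching the sensor and leaving the rest alone. On that reading there is no confounding. Much of this stands: silence about a setting is not evidence that it will differ, and a rule could sit in the figure we cannot see. But the text never says that only the sensor changes, and nominal programming with a stated base rate covers more than a sensor switch.

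The size is also open to challenge, and rightly. A floor matters only when it binds: if the sensor drives the rate above both floors, the gap does not pass through in full. Offsets can partly cancel across patients. The outcome is described as a change, and a constant offset cancels if change is taken from same-mode rest. The reference rate is undefined, however, so that protection is not secured. Nor does the 70% pacing criterion show that the pacing occurs at the base rate, since sensor-driven beats may count as well. The mental-stress figures in Section 10.0 come without resting rates by mode, so the pilot comparison above covers the ANSAR tests only.

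A reader might infer that the trial's contrast is not a sensor contrast at all, or that a quarter to all of the planned effect is bias. The documents support neither. They allow unequal settings but do not show that they will occur, and the percentages follow entirely from assumed inputs.

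**Conclusion.** The point holds in limited form. The available text governs non-sensor settings in one mode only and has no rule that equalises them within a patient. As written, a heart-rate or aerobic-capacity difference cannot be attributed to the sensor alone. The size is unknown: the 2.5 to 10 bpm in the working are upper bounds that assume a 10 bpm gap, one direction and full pass-through, and zero is equally compatible with the documents. The false-positive rates rest on the same assumptions, together with analysis of absolute heart rate. The pilot table shows sensitivity, not cause. This is a cheap improvement. Confidence is moderate, because one figure is not available and a natural reading of the crossover step would avoid the problem.

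**What to change.** Reconcile the CLS-on rules in Section 6.0 with the CLS-off definition in Section 5.0. State that, for each patient, the non-sensor settings chosen by the investigator (base rate, maximum sensor rate and the like) are the same in both periods, whichever mode comes first, so that only the active rate sensor differs. Which values to use stays with the investigator. If the figure in Section 6.0 already contains such a rule, repeat it in the text.

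Record the programmed values at the start of each period and at each test visit, so that the match can be checked and departures reported.

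The cost is a one-paragraph amendment and a short checklist at visits already planned. The small downside is that some patients may spend one period on settings slightly different from what the site would otherwise have chosen for that mode.

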#### 8.0 Reporting of Adverse Events (AE) or Unanticipated Problems involving Risk to Participants or Others

AES will be reported to the IRB according to the IRB policies and procedures.

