#### 9.0 Study Withdrawal/Discontinuation

Subjects may withdraw from the study at any time. Subjects will be unblinded at the time of withdrawal.

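### A pacing mode stopped early for an adverse event has no scheduled primary-outcome test, and the plan neither compares such stops by mode nor says how to analyse patients tested in one mode only

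*Combined protocol and SAP*

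**What the plan says.** The primary outcome in section 2.0 is "Objective change in autonomic modulation of heart rate while randomized to CLS pacing with mental stress and ANSAR testing". Section 6.0 (Randomization) fixes when those tests happen. For the first period, "At 3 months, all subjects will undergo testing as noted below"; the same tests are repeated once three months of treatment B are complete. The text names no other test occasion. The schema figure is not shown, so this is a statement about the text only.

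The same section sets the stopping rules. In the first period, "Subjects that have any adverse events during treatment A will discontinue treatment A and immediately crossover to treatment B". In the second, "Subjects with events during treatment B will be removed from the study and unblinded". The sentence just before these reads "Patients who experience significant symptoms (extreme fatigue, debilitating palpitations, or other clinically relevant symptoms) will be evaluated by their treating physician".

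On reporting, section 8.0 says "AES will be reported to the IRB according to the IRB policies and procedures". On withdrawal, section 9.0 adds "Subjects will be unblinded at the time of withdrawal". The secondary outcomes in section 2.0 are "Increase in aerobic capacity, non-sedentary behavior, and quality of life while randomized to CLS pacing"; stopping a mode is not among them. The Statistical Analysis Plan names ANOVA or Kruskal-Wallis. It defines no analysis set and gives no rule for missing or one-period data.

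**The concern.** In a cross-over trial the treatment comparison rests on pairs: one result per patient in each mode. The stopping rules, followed as written, break the pair at the moment an event occurs, and the text provides no test before the switch or at removal.

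The loss need not be random. The symptoms that section 6.0 gives as examples, fatigue and palpitations, could plausibly reflect pacing rate. In the pilot table in section 10.0 the mean resting rate was 70.0 with CLS and 60.8 without. Only subjects are blinded, so the plan does not blind those who judge events and switch modes. If stopping depends on how a mode drives heart rate, the comparison of CLS-on with CLS-off could be selective. If it does not, the cost is lost data. Either way, a difference in tolerability between the modes would be informative, and it is not a planned result.

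**Working it through.** **Inputs.** From section 10.0: 57 enrolled, target 40, drop-out 30%, assumed difference 10 and within-patient standard deviation 10 (taken here as bpm). From section 6.0: the test times and stopping rules. Not in the documents, so assumed: a stop probability *p* per period, independent between periods, of 5%, 10% or 15%; and a departure *d* of 5 or 10 bpm between the untested responses in one mode and what a model would predict for them.

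**1. The plan's own figures.** 40 / (1 − 0.30) = 57.1, which agrees with 57 (58 if rounded up). The allowance is 57 − 40 = 17 patients. For power, the standard error is 10 × √(2/N) with N − 2 degrees of freedom. This gives 96.2% at N = 30 (stated 96%), but 99.2% at N = 40 (stated 80%) and 91.1% at N = 24 (stated 81%). That mismatch is a separate matter, and this point does not depend on it.

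**2. Tracing a patient through the rules.**
- Event in A: switched at once, with no test in the first mode. At calendar month 3 the patient is already in the other mode, and the text does not say what a test on that day would count towards. The requirement to test all subjects at 3 months therefore does not supply the missing value.
- Event in B: the first-mode tests exist, but the patient leaves without a second-mode test.

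**3. Patients without a complete pair.** Lacking at least one test = 57 × (1 − (1 − p)²); both tests = 57 × (1 − p)²; neither test = 57 × p².

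| p per period | at least one missing | both present | neither |
|---|---|---|---|
| 5% | 5.6 | 51.4 | 0.1 |
| 10% | 10.8 | 46.2 | 0.6 |
| 15% | 15.8 | 41.2 | 1.3 |

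With unequal rates, 15% in one mode and 5% in the other: 57 × 0.15 = 8.6 against 57 × 0.05 = 2.9 missing in the respective mode, and 57 × (1 − 0.85 × 0.95) = 11.0 with at least one missing. The 30% allowance is used up when (1 − p)² = 0.70, that is at p = 1 − √0.70 = 16.3%.

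**4. Shift in the all-patient difference.** If only one mode's untested responses depart, the shift is p × d.
- d = 10: 0.5, 1.0 and 1.5 bpm at 5%, 10% and 15%.
- d = 5: 0.25, 0.5 and 0.75 bpm.
- Upper case, all 17 allowed drop-outs stopping in the same mode: 17/57 = 0.298, giving 3.0 bpm for d = 10 and 1.5 bpm for d = 5.

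**5. Does a mixed model cure it?** A simulation used 570 patients per run to cut noise, 40 runs, a true difference of 10 before the shift, and between- and within-patient standard deviations of 10. With 15% missing in CLS-on, 5% missing in CLS-off, and the missing CLS-on responses 10 bpm lower, the model gives 10.1. The all-patient value is 10 − 0.15 × 10 = 8.5. The model keeps one-mode patients in the analysis, but it does not correct stopping that depends on the unseen response.

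**The case against.** The other side has a good deal right.

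- *These patients are not left without a rule.* Section 6.0 says what happens to them (cross over, or leave), and section 8.0 sends adverse events to the IRB. That stands. The gap is in testing, analysis and comparison by mode.
- *Nothing is thrown away.* A reader might infer that the plan discards these patients' data. It does not say so. A patient removed in B already has the full A tests, and device activity is tracked in both periods. What is lost is one end-of-period test per stop; whether the remaining results enter the analysis is simply unstated.
- *Numbers are protected.* At 5% to 15% stopping, 41 to 51 complete pairs remain, above the target of 40. Even with 20% stopping per period on top of 30% other drop-out, about 25 pairs remain (57 × 0.70 × 0.64 = 25.5), with 92% power on the stated inputs. That stands: power is not the issue. But an allowance for numbers does nothing about loss that differs by mode.
- *The trigger may be narrower than it reads.* Taken with the preceding sentence on significant symptoms, the rule may not be meant for every trivial event. That is possible, and it affects how often stops occur. On either reading, a stopped mode has no scheduled test.
- *An early test may measure the event.* Heart-rate response taken during palpitations or severe fatigue may reflect the episode rather than the mode. This is a fair limit on the remedy, so early tests need a flag.

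**Conclusion.** The point holds as a gap in design and analysis, of minor to moderate severity. Followed as written, the rules produce event-driven loss of the paired primary outcome. Stops are not compared by mode, and the Statistical Analysis Plan does not say how to analyse patients tested in one mode.

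A reader might go further and infer that the CLS comparison will be biased. The documents do not support that: they give no event rate, no link between events and response, and no direction. All sizes here rest on assumed stop rates, independence between periods, and an assumed 5 or 10 bpm departure. On those assumptions about 6 to 16 of 57 patients lack a pair and the difference moves by at most 1.5 bpm, or 3.0 bpm in the upper case. Neither would remove a 10 bpm effect: at 15% stopping, that would take a departure of 10 / 0.15 = 67 bpm. The case for change is that the loss is partly avoidable and the analysis choice is left open.

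**What to change.** Leave the safety trigger and the physician's discretion to switch unchanged, and amend the protocol and analysis plan as follows.

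1. **Stopping visit.** Before reprogramming and unblinding, collect the quality-of-life questionnaire and download stored device activity. Do the ANSAR and mental stress tests only if safe and without delaying the switch. Flag them as early tests, since they follow less than three months in the mode and may reflect the event itself.
2. **Analysis set and model.** State that everything collected before a stop stays in the analysis, including the A tests of patients who stop in B. Analyse all patients with at least one test, by the mode in place at testing, in a mixed model with mode, period, sequence and a random patient effect.
3. **Reporting.** Report stops for adverse events by mode.
4. **Sensitivity analysis.** Because the model does not correct outcome-related stopping, shift the missing responses in CLS-on only, then in CLS-off only, by −10, −5, +5 and +10 bpm.

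The cost is wording and possibly one added visit for stops in B; the instruments are already in the study. Some tests will follow shorter exposure or be done during symptoms. Patients too unwell to test will still be missing, which is why item 4 is needed.
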